5.2 Promising specimens for TB diagnosis using Xpert Ultra

Urine

Although there is no recommendation on the use of urine as a sample for Xpert TB testing, several diagnostic accuracy studies have shown an important added yield when used in hospitalized patients. Studies by Lawn in South Africa^{28,29}, showed that Xpert testing in urine among newly admitted unselected HIV-positive adults improved bacteriological confirmation relative to sputum Ultra,

This project is part of the EDCTP2 programme supported by the European Union

sputum culture or urine LF-LAM. Xpert in urine provided the highest incremental diagnostic yield, with high specificity when used combined with sputum testing.^{28,29} A recent clinical trial by Gupta-Wright and colleagues showed a lower diagnostic yield of urine-Xpert compared to TB LAM³⁰, although it was the only test positive in 6% of microbiologically confirmed patients in the intervention arm.

Another analysis in a South African cohort of unselected HIV-positive hospitalized patients, showed a sensitivity of Urine Xpert of 41.8% (59/141) against a microbiological reference standard, very similar to that of AlereLAM (43.3% 61/141).³¹ Interestingly, 15 cases detected with Urine Xpert were not detected with Alere LAM and 17 cases were detected with AlereLAM, but not with Urine Xpert.

Stool

Similarly to urine, no recommendation has been made about the use of Xpert or Ultra in stool so far. However, recent studies on stool Xpert in pediatric pulmonary TB suggest that it could be helpful in paucibacillary TB patients. A metanalysis showed the sensitivity and specificity of stool Xpert in 67% and 99%, respectively, being higher in HIV positive children³², and other groups have reported a greater sensitivity (73%) compared to traditional tools³³. Moreover, Xpert Ultra showed higher sensitivity in stool compared to Xpert³⁴. While results of stool Xpert in adults are promising, showing a sensitivity of 90.2%-100% and specificity of 100%³⁵ and 81% in smear-negative patients³⁵, data is limited. Results of alternative in-house PCR show promising value in stool support of this specimen for PTB diagnosis (sensitivity 95-97% in smear positive and 77% in smear negative^{33,36} and 69% for EPTB³³). Although there are no published reports on HIV positive admitted patients, the abovementioned data suggest that the use of stool as a specimen for TB diagnosis could provide additional diagnostic yield in this vulnerable population.

5.3 Other promising tests and specimens

The Fujifilm SILVAMP TB LAM (FujiLAM)

A urine-based test which also detects LAM in urine, has shown promising results in frozen samples and is currently undergoing prospective evaluations in several settings. Recently published results using biobanked samples from studies conducted in South Africa showed higher sensitivity of FujiLAM compared to AlereLAM (70.4% vs 42.3%, using a microbiological reference standard), while maintaining high specificity.³¹ FujiLAM performance includes a 5-step procedure according to manufacturer's instructions and takes around 50-60 minutes from sample collection to results availability. Thus, it is also considered a true point of care test, since results could easily be handed out the same day the patient provides the sample.

This project is part of the EDCTP2 programme supported by the European Union

Given the substantially improved sensitivity of FujiLAM compared to AlereLAM, it could easily be the best test for immunosuppressed HIV positive patients, and has the potential for being an important tool for TB diagnosis in this population subgroup. In addition, it might have a potential to impact on mortality. A recent study in South Africa showed that FujiLAM conducted retrospectively predicted TB mortality among hospitalized patients.³⁷ However further studies in different populations and settings, with endpoints including patient important outcomes are needed to further assess its impact where it is most needed. The FujiLAM assay is undergoing a version change for large scale manufacturing. The new version will not be available until the end of the planned trial, so analysis for FujiLAM will be done retrospectively on banked urine samples collected as part of this study.

Oral swabs

As sputum can be difficult to collect in some patient groups, alternative specimens for TB diagnosis have been evaluated in recent years. In 2015, a study conducted in South Africa³⁸ demonstrated the presence of *M.tb* in oral swabs. The diagnostic performance of this sample collected in tongue dorsum that two samples per subject showed a combined sensitivity of 92.8% and specificity of 91.5%.³⁹ A recent study⁴⁰ showed lower sensitivity and specificity when collecting tongue swabs on different days (88%-94.4% and 79.2%, compared to sputum Xpert). However, despite these promising results, further validation studies are needed to assess the potential utility of these innovative specimens.

CRP

C-reactive protein (CRP) indicates inflammation and can be detected on capillary blood. WHO has recently recommended CRP as a method for TB screening among ambulant people living with HIV who are newly in care and not yet on antiretroviral treatment, based on similar sensitivity and specificity to symptom screening in HIV-positive populations⁴¹.

LumiraDx

LumiraDx is a recently developed point-of-care instrument that is currently available for SARS-CoV-2 testing in anterior nasal specimen, Dimer-D and CRP quantification in venous blood (<https://www.lumiradx.com/us-en/what-we-do/diagnostics/test-technology/>). While its use has not yet been tested for TB, the company is developing a *Mtb* kit to be tested in tongue swabs. LumiraDx is a fast (10min) and easy-to-use device, with potential for adding innovative POC solutions to TB diagnosis.

This project is part of the EDCTP2 programme supported by the European Union

6. Aim and hypothesis

The overall aim of this study is to assess the potential of an expanded TB testing strategy to increase the number of HIV-positive patients with microbiologically diagnosed TB who are started on treatment in adult wards of sub-Saharan Africa.

Previous studies have shown that Xpert testing of urine and stool are capable of confirming *Mtb* in patients who would otherwise test negative with traditional sputum-based methods. Evidence shows that these diagnostics may detect additional cases that are not detected by AlereLAM. Thus, an algorithm using the different tests (sputum Ultra, urine Ultra and stool Ultra) offered as a screening intervention to admitted HIV positive patients should increase the *Mtb* bacteriological yield (compared to current WHO recommended screening and testing strategies**) and contribute to earlier initiation of TB treatment. Given that some detected cases may not present with classical TB symptoms at the time of hospitalization, we believe that this strategy will increase the overall number of patients with diagnosed TB and started on treatment and ultimately reducing mortality.

*** Current WHO recommended strategies include sputum Xpert Ultra MTB/RIF whenever the patient has TB attributable symptoms, and urine Alere TB-LAM, if patients have signs and symptoms of TB, or with advanced HIV disease (1) or who are seriously ill (2) or else irrespective of signs and symptoms of TB and with a CD4 cell count of less than 200 cells/mm³. These interventions will constitute the "control arm" across all study sites. Note that the current WHO recommended strategies might not be currently applied in a standardized manner as part of the local standard of care.*

6.1 Benefit/Risk Assessment

The study poses participants with minimal or no risk, given that no experimental intervention is provided to participants, but rather to samples from participants. The potential risks are associated to those associated to blood drawn, or discomfort produced while providing the sputum, urine or stool samples. The benefits of the study include probability of earlier confirmatory diagnosis of tuberculosis, which would allow immediate treatment initiation. This might have an impact on mortality in the first two months after enrolment. These benefits need to be confirmed as they are endpoints of the study. The study would surely allow a close clinical follow-up by study staff during the participants' involvement in the clinical trial.

This project is part of the EDCTP2 programme supported by the European Union

7. Objectives

Primary Objective(s)

- To investigate the effect of an expanded TB screening strategy among HIV-positive patients admitted to hospital (including sputum Ultra, urine AlereLAM and urine and stool Ultra assay) on the proportion of microbiologically-confirmed TB cases starting treatment within 72 hours of enrolment, compared to Ultra testing (on sputum/any tissue) and AlereLAM (on urine) in only those patients who are symptomatic for TB or fulfill WHO testing recommendations

Secondary Objectives

- to assess the impact of this screening strategy on 2-month all-cause mortality.
- to assess the feasibility of multiple specimens' collection for TB diagnosis within 72hours of enrolment.

Exploratory Objectives

- To assess the added yield of a molecular TB assays (Xpert Ultra and/or LumiraDx) tongue swabs, and urine FujiLAM testing in microbiological TB confirmation
- To assess the diagnostic accuracy of CRP in blood compared to TB symptoms screening in those with microbiologically confirmed TB.
- To compare the bacteriological confirmation rate of our control arm (Ultra on sputum/any tissue and AlereLAM in only those patients who are symptomatic for TB or fulfill WHO testing recommendations) to local standard of care (current testing algorithms implemented at the participating sites before study initiation).

This project is part of the EDCTP2 programme supported by the European Union

8. Endpoints

8.1 Primary Endpoint(s)

The primary endpoint is:

- The proportion of participants diagnosed with microbiologically confirmed TB and started on TB treatment within 72 hours of enrolment, separately for intervention and control arm. The numerator is the number of participants per study arm who are diagnosed with microbiologically confirmed TB and start on treatment within 72 hours of enrolment. The denominator is the number of participants enrolled per study arm. We will compare this indicator between both study arms. Patients are defined to have microbiologically confirmed TB if at least one confirmatory TB test (Ultra, AlereLAM) gives a positive result.

Hospitalized PLHIV experience high mortality and TB underdiagnosis and misdiagnoses are frequent. TB diagnosis is important when you can quickly start appropriate therapy. This endpoint will capture both diagnostic dimensions of the intervention (higher rates of *Mtb* laboratory confirmation) as well as the relevant patient outcome (TB treatment initiated).

Diagnostic procedures and treatment initiation (if appropriate) should be completed within 72 hours of enrolment given the intervention is aimed at rapid collection of samples for all patients upon admission and that Ultra testing can provide results within a few hours from specimen collection at all participating sites.

The numerator of the primary endpoint also includes patients whose bacteriological confirmation might arrive after 72 hours of enrolment. There might be cases where liquid or solid culture might be requested and results arrive after 72 hours. If the patient had been put on treatment empirically (before a positive culture results has arrived), that case will contribute to the numerator, given that treatment would have been started in a "true" TB case.

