10.7 Minimisation of Error and Bias

Selection bias will be minimized by a) the randomization process and b) consecutive enrolment of participants meeting inclusion criteria (and not meeting exclusion criteria). Study staff from all sites will be trained prior to study initiation in order to guarantee that inclusion and exclusion criteria and

This project is part of the EDCTP2 programme supported by the European Union

well understood and applied homogenously across sites.

Other potential sources of bias (ascertainment, information, interpretation), will be also addressed. Laboratory procedures will be standardized across sites, using the same laboratory SOPs and specific lab training, in order to minimize differences by site. Given that most tests are different by arm, and that AlereLAM will be preferably done at the health facility (by the bed side), no blinding of attending physician or lab technologist will be possible. In order to explore the differences between WHO recommended procedures and real standard of care at the sites, there is an exploratory objective aiming at assessing the current yield of TB investigations under routine conditions prior to the study initiation at all sites. This will be consecutive collection of retrospective data from PLHIV admitted at participating hospitals prior the start of the study. The quality and completeness of this data might differ from participating sites.

Decision to start TB treatment will be based on any test results and the criteria of the physician responsible for the patient's care.

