10.9 Arm-specific procedures (See table 2)

10.9.1 Intervention arm

The intervention arm for this trial will consist of testing sputum, stool and urine with Ultra and urine with AlereLAM in all recruited patients regardless of symptoms. Thus, all patients allocated to this arm will be asked to provide urine, stool and/or sputum.

This project is part of the EDCTP2 programme supported by the European Union

If urine or sputum cannot be provided spontaneously at the time of recruitment, participants will be asked to do so within 72 hours (aim: within 24 hours from enrolment). Patients will be encouraged to drink water to stimulate diuresis (unless contraindicated). Urine will be collected in specific containers and stored for future testing. Ultra on Stool will be performed in fresh specimen according to the KNCV SOS method³³.

Additionally, we will ask for stool and oral swabs specimen for Xpert Ultra/ LumiraDx testing.

We aim to collect all samples specified for each intervention (including those for exploratory studies) within 72 hours from enrolment. Efforts will be made to collect all samples within the first 24 hours. Time of sample collection will be specified in the sample collection log and CRF.

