10.9.2 Control Arm

The control arm screening and testing strategy will consist of:

Sputum Ultra whenever the patient has cough, fever, weight loss or night sweats and/or *Ultra on any tissue* (including lymph nodes) from patients with suspected extrapulmonary TB.

Urine Alere TB-LAM, if patients 1) have signs and symptoms of TB (pulmonary and/or extrapulmonary), or 2) have advanced HIV disease* or 3) are seriously ill**. The latter two are all irrespective of signs and symptoms of TB.

*Adult patients with advanced HIV disease are those with CD4 cell count <200 cells/mm³ or a WHO clinical stage 3 or 4 event at presentation to the clinic.

**A seriously ill patient is any individual with HIV or of unknown HIV status presenting with one or more of the following danger signs:

- Unable to walk unaided
- A respiratory rate over 30/min
- A fever of more than 39°C, and/or
- A pulse rate of over 120/min

Thus, sputum and urine collection will only be conducted for Ultra and AlereLAM testing if the above-mentioned symptoms/criteria are present. Otherwise, urine alone will be collected in specific containers and stored for future testing. Patients will be encouraged to drink water to stimulate diuresis (unless contraindicated).

The control arm for this trial follows WHO recommendations (as of January 2020) for bacteriological testing among hospitalized HIV-positive individuals.

This project is part of the EDCTP2 programme supported by the European Union

Study staff will collect the samples for both arms.

In case any sample cannot be obtained within the first 72 hours from enrolment, reasons should be recorded in the appropriate CRF. In case the participant can provide the required sample(s) after 72 hours from enrolment, samples should still be collected and processed with clear indication of date and time. Special measures need to be implemented locally so the laboratory is aware of the tests to be performed despite some potential delay in specimen testing. After 72 hours from enrolment have passed, patient will be managed as per national guidelines.

Other than TB, patient clinical management will follow established national guidelines and protocols for hospitalized HIV-positive patients.

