| TB Investigations | | Sputum Ultra | | | | | |
| | Urine | Stool | | | | | |
| | AlereLAM# | Ultra | | | | | |
| | Sputum Ultra* | Urine Ultra | | | | | |
| Samples collected and tests | Blood CD4 | Urine AlereLAM | | | | | |
| | | 2x Oral Swabs | | | | | |
| | | Urine FujiLAM | | | | | |
| | | Blood CD4 | | | | | |
| | | Blood for CRP | | | | | |
| Results issued | | | | X | | | |
| Further contacts | | | | | | | |
| Verification TB diagnosis / ad hoc TB investigations | | | | X | X | X | X |
| Verification TB treatment initiation | | | | X | X | X | X |
| Verification vital status | | | | X | X | X | X |
| HIV care / ART | | | | X | X | X | X |

*Sputum Ultra whenever the patient has cough, fever, weight loss or night sweats and/or Ultra on any tissue (including lymph nodes) from patients with suspected extrapulmonary TB

#Urine LAM if patients have currently signs and symptoms of TB (pulmonary and/or extrapulmonary), or with advanced HIV disease (1) or who are seriously ill (2) or else irrespective of signs and symptoms of TB and with a CD4 cell count of less than 200 cells/mm³.

[&]CD4 count testing will be done if not available within the last 3 months. Most recent viral load will be captured (if available)

**urine should be collected in all participants in the control arm, irrespective of whether LAM test is done.

This project is part of the EDCTP2 programme supported by the European Union

12. Laboratory procedures and storage of samples

Samples will be processed and results issued back to attending physicians as soon as possible. AlereLAM results should be available within two hours from specimen collection. Ultra results should be provided within 24 hours from being collected at the participating hospital laboratory associated facilities.

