The primary efficacy endpoint has a composite numerator 'microbiologically confirmed TB and therapy initiated within 72 hours from admission' (success), 'non lab-confirmed TB or therapy

This project is part of the EDCTP2 programme supported by the European Union

not initiated within 72 hours' (failure).

Microbiological confirmation may arrive later than 72 hours after enrolment (to account for scenarios in which culture is requested or there is any delay on sample processing).

The primary efficacy analysis will be compared between the proportion of microbiologically confirmed TB and therapy initiated within 72 hours of enrolment in each study arm.

Adjustment for other variables (country, hospital, seasonality or other possible confounders) may be considered and will be described in detail in the analysis plan.

Missing values will be examined in detail. We may consider a multiple imputation procedure if necessary (variables with more than 10% of missing values).

We will accept as significant difference the p-values less than 0.05.

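### SAP 4.4 times the primary outcome by Ultra result receipt, while Protocol 8.1 and 13.2.2 put the 72-hour limit on treatment start only

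*Protocol*

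**What the plan says.** Protocol 8.1 defines the primary as the proportion of all enrolled participants who have confirmed TB and start treatment within 72 hours. Confirmation is defined by test result, with no time limit: "Patients are defined to have microbiologically confirmed TB if at least one confirmatory TB test (Ultra, AlereLAM) gives a positive result". The section then adds: "The numerator of the primary endpoint also includes patients whose bacteriological confirmation might arrive after 72 hours of enrolment". Protocol 13.2.2 repeats the rule under the efficacy analysis: "Microbiological confirmation may arrive later than 72 hours after enrolment". It gives two reasons, a culture request or any delay in processing the sample.

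SAP 3.4.1, 7.2 and 8.1 carry the same composite and attach the 72 hours to the start of treatment, but none of them says what happens when the result is late.

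The Hospitalization Assessment table in SAP 4.4 contains two items that bear on timing:

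- For the date and time of receipt of the sputum Ultra and urine Ultra results, the stated use is to compute the time to result and to classify the primary outcome as at most 72 hours or more than 72 hours.
- HOSP_TB_TX_72H_YN asks, for confirmed patients, whether treatment began within 72 hours.

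On timing in the field, Protocol 10.9.1 says: "We aim to collect all samples specified for each intervention (including those for exploratory studies) within 72 hours from enrolment". Protocol 12 says: "Ultra results should be provided within 24 hours from being collected".

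**The concern.** An analyst who codes the primary from the SAP meets a note that applies the 72-hour cut to result receipt. An analyst who codes it from the protocol applies the cut to treatment only. For some patients the two codings give opposite outcomes on the primary endpoint of an unblinded trial, so the rule should be settled before the data are seen.

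The disagreement need not be balanced. The note names sputum and urine Ultra only. Under Protocol 10.9, urine Ultra is routine in the intervention arm and is not part of the control strategy. In the control arm, "Thus, sputum and urine collection will only be conducted for Ultra and AlereLAM testing if the above-mentioned symptoms/criteria are present". Successes lost to the note could therefore come mainly from the intervention arm, which would shrink the observed difference.

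**Working it through.** **Step 1. Can the two rules disagree on schedule?** Samples may be taken up to 72 h (Protocol 10.9.1) and an Ultra result may follow 24 h later (Protocol 12). The latest on-schedule receipt is 72 + 24 = 96 h. Treatment may begin before the result, because "Decision to start TB treatment will be based on any test results and the criteria of the physician responsible" (Protocol 10.7).

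Take a patient treated at 60 h, with a positive Ultra received at 80 h and no other positive test:

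| Source | 72 h limit applies to | Outcome |
|---|---|---|
| Protocol 8.1, 13.2.2 | treatment start | success |
| SAP 4.4, HOSP_TB_TX_72H_YN | treatment start | success |
| SAP 4.4, Ultra receipt-time note | result receipt | failure |

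SAP 4.4 therefore also disagrees with itself. A patient with an AlereLAM or other positive result in time is not affected.

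**Step 2. Reproduce the planned size.** Inputs from SAP 5: 19% vs 26%, two-sided alpha 0.05, power 80%, 5% loss. With p̄ = (0.19 + 0.26)/2 = 0.225,

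n = [1.96·√(2·0.225·0.775) + 0.8416·√(0.19·0.81 + 0.26·0.74)]² / 0.07² = 557.5, so 558 per arm.

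Allowing for loss, 558 × 1.05 = 586 (558/0.95 gives 588). The plan's 586 is reproduced.

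**Step 3. Power under the protocol rule.** With n = 586 per arm,

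power ≈ Φ{[|p₂ − p₁|·√n − 1.96·√(2p̄(1 − p̄))] / √(p₁(1 − p₁) + p₂(1 − p₂))}.

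For 0.19 vs 0.26 this is 81.9%. The exact binomial rejection probability of the pooled z test is 82.0%.

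**Step 4. Power under the SAP 4.4 note.** Let q be the share of protocol-defined successes whose only positive result is a sputum or urine Ultra received after 72 h. The documents give no value for q, so 2% to 10% is an assumption. The success rates become 0.19(1 − q_c) and 0.26(1 − q_i). Exact power at 586 per arm:

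| q_c | q_i | Control | Intervention | Difference | Power |
|---|---|---|---|---|---|
| 0 | 0 | 19.0% | 26.0% | 7.0 points | 82% |
| 2% | 2% | 18.6% | 25.5% | 6.9 | 81% |
| 5% | 5% | 18.1% | 24.7% | 6.7 | 80% |
| 10% | 10% | 17.1% | 23.4% | 6.3 | 77% |
| 0 | 2% | 19.0% | 25.5% | 6.5 | 76% |
| 0 | 5% | 19.0% | 24.7% | 5.7 | 66% |
| 0 | 10% | 19.0% | 23.4% | 4.4 | 45% |

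In patients, q_i of 2%, 5% and 10% is 586 × 0.26 × q_i = about 3, 8 and 15 intervention successes recoded as failures.

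**Step 5. Can the note work as a rule at all?** SAP 4.4 lists receipt times for sputum and urine Ultra and result times for AlereLAM. For stool and other-specimen Ultra it lists results but no result times. The note therefore cannot be applied evenly to every test that counts as confirmation.

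**The case against.** The best reply is that the note is loose wording in a column describing how variables are used. Every formal definition of the primary in both documents ties the limit to treatment. Result times have a proper use, because the per-protocol set in SAP 6.1.1 requires results within 72 hours. The 96-hour case is also the outer limit: collection is aimed for within 24 hours and AlereLAM should be read within two. This stands as far as likelihood goes. It supports a small q and makes the intervention-only 10% case extreme. It does not remove the conflict, because the note names the primary outcome, not the per-protocol set, and the SAP never states that late confirmation counts.

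One could also say that the late-confirmation rule was meant for culture, which is the example in Protocol 8.1. Protocol 13.2.2 answers this by including any processing delay.

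A reader might go further and infer that a positive primary would be hollow: empirically treated patients could be confirmed only by the extra stool and urine tests, so the endpoint could rise with nobody extra treated. The documents do not support this as a defect. The aim (Protocol 6), the objective (7) and the rationale (8.1) all concern confirmed cases starting treatment. The wider expectation, "we believe that this strategy will increase the overall number of patients with diagnosed TB and started on treatment", is stated as a belief in Protocol 6, and treatment irrespective of confirmation is already a planned secondary (SAP 8.2.4). How much empirical treatment would be reclassified depends on rates the documents do not give.

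Nor does it follow that the SAP omits the primary from its results. SAP 8.1 commits to a risk difference and 95% confidence interval. Table 4 shows no explicit composite row as read, but its confirmed-TB row may sit under the 72-hour treatment row, as in Table 3, with the indentation lost in extraction.

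**Conclusion.** The concern holds for one note. The receipt-time entry in SAP 4.4 contradicts Protocol 8.1 and 13.2.2 and the treatment-timing item in the same SAP table. Followed literally, it turns some protocol-defined successes into failures. The size depends on q, which is unknown. For q of 2% to 10%, power goes from 82% to between 81% and 77% if both arms are affected equally, and to between 76% and 45% if only the intervention arm is. The second range is a bound, not an expectation, since sputum Ultra is used in both arms. All figures assume that 26% and 19% are the true rates under the protocol rule. The effect is to dilute a real difference. The labelling of Table 4 is a minor point.

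**What to change.** 1. In SAP 4.4, replace the receipt-time note with: *The 72 h limit of the primary applies to treatment start only; a positive Ultra or AlereLAM result received after 72 h still counts as confirmation. Result times are used for time to diagnosis and the per-protocol set.*
2. Add result date and time for stool and other-specimen Ultra, for those same two uses.
3. Minor: label the rows of Table 4 so that the composite (confirmed TB and treatment within 72 h) is shown as the primary, with its risk difference and 95% confidence interval.

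Reporting SAP 8.2.4 next to the primary is an optional choice of presentation.

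The cost is SAP wording and a few fields. Protocol 14.3 already has sites log when test results are received. Sample size, primary test and alpha are unchanged.
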